11.1 Data Monitoring Committee

An external data monitoring committee (DMC) composed of persons independent of AbbVie and with relevant expertise in their field will review unblinded safety data from the ongoing study. The primary responsibility of the DMC is to protect the safety of the subjects participating in this study.

A separate DMC charter describes the roles and responsibilities of the DMC members, frequency of data reviews, relevant data to be assessed, and general operations.

12.0 Overall Type-I Error Control

Overall Type I error control is not planned for this Phase 2 study.

13.0 Version History

Table 5. SAP Version History Summary

Version	Date	Summary
1.0	17 April 2022	Original version
2.0	10 February 2023	
 • Provided clarification that PGIC-CD+, PGIS-CD+, and data collected in the Wearable Device Substudy are not in the scope of the SAP, removed endpoints related to PGIC-CD+, PGIS-CD+ and the endpoints from the Wearable Device Substudy from SAP (Section 1.0, Section 3.4). • To be more precise in terms of definition of study populations.

Version	Date	Summary
		
 ○ Updated the population attribute to target population (Section 2.1, Table 1, Table 2) ○ Specified the terminology of ITT1 population (Section 4.0) ○ Provided additional clarifications on the definition of ITT3 population (Section 4.0) ● The following changes have occurred to reflect changes in the protocol amendment to add Rescue Therapy option with ABBV-154 during the Maintenance Period and removal of the Long-Term Extension study. 
 ○ Provided description of ABBV-154 rescue therapy (Section 2.2, Figure 1) ○ Added ITT3-RES and SA-RES for the efficacy/safety analyses on the subjects who receive Rescue Therapy option with ABBV-154 (Section 4.0, Section 10.1) ○ Added the analyses to evaluate the efficacy of ABBV-154 rescue therapy (Section 9.8) ○ Provided clarification that TEAEs for the Maintenance Period (SA3 population) and combined period analyses (SA-INMN, SA-IN2MN population) don't include AEs with onset date after initiation of ABBV-154 rescue therapy (Section 10.2.1) ○ Added the definition of TEAE for SA-RES population (Section 10.2.1) ○ Removed language related to the Long-Term Extension study (Section 2.2, Section 9.1) ● Provided additional clarity for the timing of the primary analysis for each period (Section 2.2, Section 9.1). ● Provided additional clarification for the summary of subject disposition (Section 5.0). ● Provided clarification for the calculation of duration of treatment that only duration of blinded study drug will be considered for SA1/SA2/SA3 populations, and also provide more clarification of study drug duration of Induction Group 4 (Section 6.0).

Version	Date	Summary
		
 • Provided clarification that medications started after initiation of ABBV-154 rescue therapy will not be considered as concomitant medications for the Maintenance Period, and updated concomitant medications definition following the removal of Long-Term Extension study (Section 7.0). • Updated the handling strategy for the intercurrent event of premature discontinuation of study drug (Section 8.2, Section 9.2.1, Table 1, Table 2). • Provided additional clarity that data from subjects randomized to Induction Group 1, considered as responder at Week 12 of the Induction Period and entered the Maintenance Period will not be included in the comparison between ABBV-154 230 mg SC EOW versus Placebo as they are not from the same randomization (Section 9.1). • Provided clarification that data collected after initiation of ABBV-154 rescue therapy will not be included in the AO analysis (Section 9.2.3). • Provided clarification for the planned analysis method for the additional efficacy analyses (Section 9.5). • Updated the terminology "safety topics of interest" to "adverse events of special interest" and provided list of AESIs and the corresponding identification criteria (Section 10.1, Section 10.2.2, Section 10.2.6, Appendix G). • Updated TEAE definition following the removal of Long-Term Extension study, and also provided additional clarifications on TEAE definition for the SA-ALL154 population and patient-year duration calculation method for the SA-ALL154 population (Section 10.2.1, Section 10.2.4). • Updated AE severity grade to CTCAE grade to align with AE collection strategy (Section 10.2.2, Section 10.2.3). • Provided additional clarity that laboratory/vital sign collected 70 days after last dose of study drug within each analysis period will not be included in the analysis for that period (Section 10.3, Section 10.4). • Provided additional clarity that additional interim analysis may be performed for the Maintenance Period (Section 11.0).

Appendix A. Protocol Deviations

The number and percentage of subjects who reported at least one of the following protocol deviation categories will be provided.

- Subject entered into the study even though s/he did not satisfy entry criteria.
- Subject developed withdrawal criteria during the study and was not withdrawn.
- Subject received wrong treatment or incorrect dose of study.
- Subject took prohibited concomitant medication.

Appendix B. Crohn's Disease Activity Index (CDAI)

The Crohn's Disease Activity Index (CDAI) is a composite instrument that includes patient symptoms evaluated over 7 days (abdominal pain, stool frequency and general well-being), as well as physical and laboratory findings. These items are scored individually, weighted, and do not contribute equally to the overall score. The CDAI is derived from summing up the weighted individual scores of eight items as detailed below:

			Factor	Subtotal
1. Number of liquid or very soft stools (Record the frequency per day)	$\frac{\quad}{\quad} + \frac{\quad}{\quad} + \frac{\quad}{\quad} + \frac{\quad}{\quad} + \frac{\quad}{\quad} + \frac{\quad}{\quad} + \frac{\quad}{\quad} = \frac{\quad}{\quad}$ Days: 1 2 3 4 5 6 7 Sum	×	2	
2. Abdominal pain rating: 0 = none, 1 = mild, 2 = moderate, 3 = severe	$\frac{\quad}{\quad} + \frac{\quad}{\quad} + \frac{\quad}{\quad} + \frac{\quad}{\quad} + \frac{\quad}{\quad} + \frac{\quad}{\quad} + \frac{\quad}{\quad} = \frac{\quad}{\quad}$ Days: 1 2 3 4 5 6 7 Sum	×	5	
3. General well-being: 0 = generally well, 1 = slightly underpar, 2 = poor, 3 = very poor, 4 = terrible	$\frac{\quad}{\quad} + \frac{\quad}{\quad} + \frac{\quad}{\quad} + \frac{\quad}{\quad} + \frac{\quad}{\quad} + \frac{\quad}{\quad} + \frac{\quad}{\quad} = \frac{\quad}{\quad}$ Days: 1 2 3 4 5 6 7 Sum	×	7	
4. Number of 6 listed categories the subject now has Check all items that apply:  Arthritis/arthralgia  Iritis/uveitis  Erythema nodosum/pyoderma gangrenosum/aphthous stomatitis  Fissure, abscess and/or anal fistula (draining/non-draining)  Other fistula (draining/non- draining)  Fever over 100°F (37.8°C) during past week	Record "0" if no categories checked	×	20	
5. Taking Lomotil/Imodium/ Loperamide/opiates for diarrhea 0 = no, 1 = yes	_____	×	30	
6. Abdominal mass 0 = none, 2 = questionable, 5 = defined	_____	×	10	
7. Hematocrit: ____.	Male: (47 – hematocrit) = Female: (42 – hematocrit) = Subtotal If hematocrit > normal, enter "0"	×	6	
8. Body weight: ____.(kg) Standard weight: ____.(kg)	$100 \times [1 - (\text{Body wt}/\text{Standard wt})] =$ Percent below standard weight: _____ If body wt > std. wt, enter "0"	×	1	
			Total	

Higher CDAI scores indicate more severe disease. For the calculation of CDAI and components (daily stool frequency, abdominal pain score and general well-being) at each visit, the following rules will be applied:

1. Identify the visit date with CDAI components that are collected, and set it as the CDAI calculation date.
2. Calculate the subtotal scores from the component 1-3 (liquid or very soft stool frequency, abdominal pain score and general well-being) as follows:
 - a. Select the diary data from 14 days prior to the CDAI calculation date, and set the data from the 4 days (the day prior to, on the day of and two days after the endoscopy date) to missing;
 - b. Take non-missing diary data from 7 most recent days from step i. If there are multiple entries on the same day for the eDiary component, use the worst result (larger number);
 - c. If there are non-missing diary data from 7 days, the subtotal score is calculated as the sum of the 7-day scores, and multiplying the factor for the corresponding component as listed in the table above;
 - d. If there are non-missing diary data from less than 7 days but greater than 3 days (4, 5, 6 days), the subtotal score is calculated as average of the dairy data and times 7, and multiplying the factor for the corresponding component as listed in the table above;
 - e. If there are only less than 4 days of non-missing diary data available, the subtotal score will be set to missing.

Of note, Average daily SF/AP will be determined in the same way as described above to derive SF/AP-related endpoints (for example, clinical remission per SF/AP).

3. Subtotal scores for components 4-6 (Number of 6 listed categories, usage of Lomotil/Imodium/Loperamide/opiates for diarrhea and abdominal mass) will be determined using the data collected on the CDAI calculation date and the corresponding formula in the table above;

4. Subtotal score for component 7 (Hematocrit) is calculated as follows:
 - a. Identify the Hematocrit (%) value from the same visit as the CDAI calculation date, use the Hematocrit that is closest to the CDAI calculation date;
 - b. Hematocrit values obtained from previous visits can be used.
 - c. The subtotal score for Hematocrit is calculated using the formula in the table above. If Hematocrit value is greater or equal to 47% for male subjects (greater or equal to 42% for female subjects), the subtotal score is set to 0.
5. Subtotal score for component 8 (percentage below standard weight) is calculated as follows:
 - a. Standard weight is calculated based on height obtained at screening, sex and study operations manual Section [7.2](#);
 - b. Body weight is based on the measurement obtained on the CDAI calculation data, or previous visits if the measurement is missing.
 - c. The subtotal score for percentage below standard weight is calculated using the formula in the table above.
6. CDAI score is calculated as the sum of subtotal scores of 8 components, and the total CDAI score will be rounded to 1 decimal. If any of the subtotal scores are missing, the CDAI score will be missing.

Appendix C. Simple Endoscopic Score – CD (SES-CD)

SES-CD is calculated based the sum of individual segment values for four endoscopic variables (presence and size of ulcers, ulcerated surface, affected surface and presence of narrowing). Each variable in each segment be scored 0 to 3 resulting in SES-CD values ranging from 0 to 56 with higher scores indicating more severe disease.

[figure not shown]
SES-CD Scoring:

	Rectum	Sigmoid and Left Colon	Transverse Colon	Right Colon	Ileum	Total
Size of Ulcers Enter: 0 if none 1 if aphthous ulcers (0.1 to ≤ 0.5 cm) 2 if large ulcers (> 0.5 to 2 cm) 3 if very large ulcers (> 2 cm)						
Ulcerated Surface Enter: 0 if none 1 if < 10% 2 if 10% – 30% 3 if > 30%						
Affected Surface Enter: 0 if unaffected segments 1 if < 50% 2 if 50% – 75% 3 if > 75%						
Presence of Narrowing Enter: 0 if none 1 if single, can be passed 2 if multiple, can be passed 3 if cannot be passed						
					TOTAL =	

Appendix D. Patient Reported Outcomes Questionnaires Descriptions

IBDQ – Inflammatory Bowel Disease Questionnaire

The IBDQ is a 32-item (ranges 1 – 7) self-report questionnaire for patients with IBD to evaluate the patient reported outcomes across 4 dimensions: bowel symptoms (loose stools, abdominal pain), systemic symptoms (fatigue, altered sleep pattern), social function (work attendance, need to cancel social events), and emotional function (anger, depression, irritability). The IBDQ total Score ranges from 32 to 224 with a higher score indicating better outcome.

The derivation of the IBDQ total score and the four IBDQ domain scores are as follows:

Domain Scores:

S1. BOWEL SYMPTOM: Q1 + Q5 + Q9 + Q13 + Q17 + Q20 + Q22 + Q24 + Q26 + Q29
[score ranges from 10 - 70],

S2. SOCIAL FUNCTION: Q4 + Q8 + Q12 + Q16 + Q28

[score ranges from 5 - 35],

S3. SYSTEMIC SYMPTOM: Q2 + Q6 + Q10 + Q14 + Q18

[score ranges from 5 - 35],

S4. EMOTIONAL FUNCTION: Q3 + Q7 + Q11 + Q15 + Q19 + Q21 + Q23 +
Q25 + Q27 + Q30 + Q31 + Q32

[score ranges from 12 - 84].

Total Score:

IBDQ Total Score = SUM of (bowel symptom domain score, social function domain score, systemic symptom domain score, emotional function domain score).

The following convention applies to IBDQ:

When not more than 20% of items in a domain of IBDQ were missing, it was substituted with the mean values from the items completed in the particular domain; otherwise, they were treated as missing. The 20% threshold in each domain is: bowel symptom domain: 2 items, systemic symptom domain: 1 item, social function domain: 1 item, emotional function domain: 2 items. If any of the 4 domain scores is missing, the total IBDQ score will be set to missing.

SF-36 – Short Form 36

The SF-36 questionnaire is a self-administered multi-domain scale with 36 items. Eight subscales cover a range of functioning: physical functioning, role-physical, bodily pain, general health, vitality, social functioning, role-emotional, and mental health. The scoring yields a physical component score, a mental component summary score, and subscale scores. Higher scores represent better outcomes. The concepts measured by the

SF-36 are not specific to any age, disease, or treatment group, allowing comparison of relative burden of different diseases and the benefit of different treatments.

FACIT-F – Functional Assessment of Chronic Illness Therapy-Fatigue

The Functional Assessment of Chronic Illness Therapy (FACIT) measurement system is a comprehensive compilation of questions that measure health related quality of life in patients with cancer and other chronic diseases (www.facit.org). The FACIT-F scale is a symptom-specific subscale of FACIT and is composed of 13 fatigue-related questions as follows. The response to each question is as follows: 0=Not at all, 1=A little bit, 2=Somewhat, 3=Quite a bit, 4=Very much.

1. I feel fatigued
2. I feel weak all over
3. I feel listless ("washed out")
4. I feel tired
5. I have trouble starting things because I am tired
6. I have trouble finishing things because I am tired
7. I have energy
8. I am able to do my usual activities
9. I need to sleep during the day
10. I am too tired to eat
11. I need help doing my usual activities
12. I am frustrated by being too tired to do the things I want to do
13. I have to limit my social activity because I am tired

In order to have higher values representing lower level of fatigue, all of the items, except for item 7 "I have energy" and item 8 "I am able to do my usual activities," are assigned reversed scores: reversed score = 4 – raw score. The total FACIT-F score will then be calculated as follows:

- FACIT-F score = $13 \times [\text{Sum of answered-item scores} / \text{Number of items answered}]$

The score ranges from 0 to 52, 52 being the lowest level of fatigue.

When there are missing data, provided that more than 50% of the items (i.e., at least 7 of 13 items) were answered in FACIT-F questionnaire, the total score will not be deemed as missing but be calculated as the mean response for all the non-missing-value items. If less than 50% of the items were answered, the total score will have a missing value.

Appendix E. Random Seeds

In case of non-convergence, the random seed will be updated by adding 100000 at each attempt until convergence of model happens.

Table I-1. Random Seeds for NRI-C

Variables	Random Seed	
	MCMC Procedure	PROC MI
CDAI	20371	30371
SES-CD (for 20 individual variables)	N/A	31371
SF	22371	32371
AP score	23371	33371
IBDQ total score	24371	34371
Bowl Urgency	25371	35371
Rectal Bleeding	26371	36371

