3.0 Endpoints

In Section 3.0, please note

1. "Baseline" refers to the last available measurement on/before Baseline [Week 0, Day 1] of the Induction Period;
2. All endoscopic endpoints will be scored by central review;
3. Average daily liquid or very soft stool frequency (SF) and average daily abdominal pain (AP) score (SF/AP)-based efficacy endpoints will be analyzed in

the subset of subjects with an average daily liquid or very soft SF score ≥ 4 and/or average daily AP score ≥ 2 at Baseline.

The following endpoint definitions apply to the efficacy variables described below:

- **Endoscopic response:** decrease in Simple Endoscopic Score for Crohn's Disease (SES-CD) $> 50\%$ from Baseline (or for subjects with isolated ileal disease and a Baseline SES-CD of 4, at least a 2-point reduction from Baseline)
- **Clinical remission per CDAI:** CDAI < 150
- **Clinical response (CR100):** a decrease of CDAI ≥ 100 points from Baseline
- **Clinical remission per SF/AP:** average daily very soft or liquid SF ≤ 2.8 and not worse than Baseline AND average daily AP score ≤ 1 and not worse than Baseline
- **Enhanced Clinical Response per SF/AP:** $\geq 60\%$ decrease in average daily very soft or liquid SF and/or $\geq 35\%$ decrease in average daily AP score and both not worse than baseline, and/or clinical remission per SF/AP
- **Clinical response per SF/AP:** $\geq 30\%$ decrease in average daily liquid or very soft SF and/or $\geq 30\%$ decrease in average daily AP score and both not worse than Baseline
- **Endoscopic remission:** SES-CD ≤ 4 and at least a 2-point reduction versus Baseline and no subscore > 1 in any individual variable
- **Ulcer-free endoscopy:** SES-CD ulcerated surface subscore of 0 in subjects with SES-CD ulcerated surface subscore ≥ 1 at Baseline

Details of CDAI, SES-CD and patient-reported outcome (PRO) questionnaires are provided in [Appendix B](#), [Appendix C](#) and [Appendix D](#) respectively.

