3.2 Secondary Endpoints

The following endpoints will be included as secondary endpoints:

- Achievement of:
 - clinical remission per CDAI at Week 12 in the Induction Period.
 - clinical remission per SF/AP at Week 12 in the Induction Period.
 - endoscopic response at Week 40 in the Maintenance Period.
 - clinical remission per CDAI at Week 40 in the Maintenance Period.
 - clinical remission per SF/AP at Week 40 in the Maintenance Period.

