 - Markov Chain Monte Carlo (MCMC) will be first applied to augment data into monotonic missing pattern (where applicable) and PROC MI will be used to generate 30 datasets using the regression method. If the binary endpoints are derived from the continuous variables, PROC MI will be applied to the continuous variables. The variables to be included in the imputation model are: treatment group, randomization stratification factors for the corresponding period, age, gender, weight, baseline measurement (if applicable) and post-baseline measurements at each visit for the respective analysis period up to the end of the analysis period. The random seed for MCMC and the random seed for PROC MI are specified in [Appendix E](#). The imputed post-baseline measurements will be rounded to the same precision as the observed data before the determination of responder status. Subjects will be characterized as responders or non-responders based on MI imputed data. Using the CMH model adjusted by randomization stratification factors, the endpoints will be analyzed using each of the 30 imputed datasets. SAS PROC MIANALYZE will be used to generate the final inferences of the risk difference between treatment groups, using Rubin's rule.² Note that measurements will be set to missing 1) at or after the occurrence of the CD-related confounding medications intercurrent event, or 2) on/after the date of initiation of CD-related medications after premature discontinuation of study drug before applying MI. After the MI imputation, an NRI override will be implemented for missing values 1) missing values due to reasons other than COVID-19 infection or logistic reasons, or 2) at or after the occurrence of the CD-related confounding medications or 3) on/after the date of initiation of CD-related medications after premature discontinuation of study drug, that is, regardless of MI imputed values, subjects satisfying 1) or 2) or 3) will be considered as "non-responder" for binary efficacy endpoints.

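### As the seed table naturally reads, SF and AP are imputed in separate runs; this drops their same-visit residual correlation and, if that is positive, slightly understates SF/AP clinical remission under NRI-C (minor; one merged imputation step fixes it)

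*SAP*

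**What the plan says.** SAP 3.0 defines clinical remission per SF/AP as a both-required rule: SF at most 2.8 and AP at most 1, neither worse than Baseline ("not worse than Baseline AND average daily AP score"). SAP 3.2 makes it a secondary endpoint in Induction ("clinical remission per SF/AP at Week 12 in the Induction Period") and again at Week 40 of Maintenance. SAP 9.4.1 makes NRI-C the primary missing-data approach for these endpoints.

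Under NRI-C, multiple imputation fills only data missing because of COVID-19. All other missing data, and data after confounding or other CD medication, become non-response. On what is imputed, SAP 9.2.1 says: "If the binary endpoints are derived from the continuous variables, PROC MI will be applied to the continuous variables". Its covariate list is treatment group, stratification factors, age, gender, "weight, baseline measurement (if applicable) and post-baseline measurements at each visit for the respective analysis period". It does not mention the other component of a two-part endpoint.

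Appendix E ("Table I-1. Random Seeds for NRI-C") has one row for "SF 22371 32371" and another for "AP score 23371 33371", where the two numbers are the MCMC and PROC MI seeds. By contrast, "SES-CD (for 20 individual variables") is a single row with a single PROC MI seed.

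SAP Appendix B derives average daily SF and AP from the same diary window by the same rule, so a missed visit will usually lose both.

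**The concern.** The table groups variables where one run is meant (the 20 SES-CD items) and does not group SF and AP. Two separate runs draw the two Week 12 or Week 40 values without regard to each other, apart from what each variable's own past, treatment and strata carry. For an endpoint that needs both to succeed, dropping a positive same-visit residual correlation makes joint success too rare among imputed subjects.

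SAP 9.2 says the purpose of the imputation is to estimate the treatment effect as it would be without the pandemic. An imputation model that omits the dependence the endpoint rests on serves that purpose less well than it could. The planned checks would not show the problem: NRI-NC counts the same subjects as failures, and the as-observed analysis drops them. Clinical remission per CDAI is not affected, because CDAI is imputed as one total score.

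**Working it through.** The plan gives no SF/AP remission rate, SF-AP correlation or COVID-missing share, so there is no figure of its own to reproduce. The values below are assumptions, shown over ranges.

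**Inputs**
- From the SAP: both-required rule (3.0); separate seeds (Appendix E); each run uses the variable's own measurements (9.2.1, as naturally read); 53 subjects per group in Induction and 40 in Maintenance (2.4).
- Assumed: within-visit SF-AP correlation ρ of 0.2 to 0.6; correlation r of each variable across visits of 0.5 or 0.7; Baseline plus two visits observed, last visit missing; each component succeeds with probability 0.5; COVID-missing share f of 10%.

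**Step 1. How much correlation survives separate imputation.** With three earlier values and equal across-visit correlation r, own history explains R² = 3r²/(1 + 2r).
- r = 0.5: 0.75/2 = 0.375
- r = 0.7: 1.47/2.4 = 0.6125

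When SF and AP have the same correlation ρ between subjects and within visits, the two imputed values correlate at ρR². The correlation is weakened but not removed.

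**Step 2. Joint success.** For bivariate normal variables with success probability 0.5 each, P(both) = 0.25 + arcsin(correlation)/(2π). Use ρ for the truth and ρR² for separate imputation. The simulated columns are from 400,000 subjects.

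| r | ρ | ρR² | true P(both) | separate, formula | separate, simulated | joint, simulated |
|---|---|---|---|---|---|---|
| 0.5 | 0.2 | 0.075 | 0.282 | 0.262 | 0.261 | 0.280 |
| 0.5 | 0.4 | 0.150 | 0.315 | 0.274 | 0.272 | 0.315 |
| 0.5 | 0.6 | 0.225 | 0.352 | 0.286 | 0.285 | 0.351 |
| 0.7 | 0.2 | 0.1225 | 0.282 | 0.270 | 0.270 | 0.283 |
| 0.7 | 0.4 | 0.245 | 0.315 | 0.289 | 0.289 | 0.315 |
| 0.7 | 0.6 | 0.3675 | 0.352 | 0.310 | 0.310 | 0.353 |

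Formula and simulation agree to within 0.002. The simulated shortfall for these rows runs from 1.3 points (r = 0.7, ρ = 0.2) to 6.7 points (r = 0.5, ρ = 0.6). If the visit-level noise in SF and AP is uncorrelated and only the subject-level parts correlate (0.4), it is still 1.5 points (0.282 against 0.267, r = 0.5) or 1.1 points (0.295 against 0.284, r = 0.7). Hence roughly 1 to 7 points among imputed subjects. Joint imputation recovers the truth to within 0.001.

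**Step 3. Whole-arm effect.** Arm error = f × shortfall. At f = 10%: 0.10 × 1.1 = 0.11 to 0.10 × 6.7 = 0.67 points. One subject is 1/53 = 1.9 points in Induction and 1/40 = 2.5 points in Maintenance.

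**Step 4. Risk difference.** Shift = −f × (shortfall on ABBV-154 − shortfall on placebo).
- Limiting case with no information from own history, ρ = 0.6: the shortfall is 0.083 at success probability 0.30, 0.101 at 0.45 and 0.083 at 0.70.
- Placebo 0.30, active 0.45: −0.10 × (0.101 − 0.083) = −0.18 points.
- Placebo 0.45, active 0.70: −0.10 × (0.083 − 0.101) = +0.18 points.
- Longitudinal simulation with every post-baseline visit missing and correlation 0.5: true rates 25.6% and 8.4% (difference 17.2); separate imputation 18.8% and 4.7% (difference 14.1). The shift is −3.1 points among imputed subjects, so −0.31 points at f = 10%.

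**The case against.** Several points on the other side stand.

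- **Separate runs are inferred.** No sentence says SF and AP are imputed apart, and the phrase on post-baseline measurements in 9.2.1 does not expressly exclude the other component. This is fair. The separate seeds beside one shared SES-CD row still make separate runs the natural reading, and a second programmer could not settle it from the text.
- **The sign is assumed.** With a negative correlation the error reverses: at −0.2, and with no information from own history, joint success is overstated by about 2 to 3 points.
- **The scope is narrow.** Only COVID-missing subjects are affected. SAP 9.1 plans to report how many there are for primary and secondary endpoints. NRI-C cannot give an arm rate below NRI-NC, so a lower bound on the rate is already planned.
- **Consequences are limited.** These are secondary endpoints in a Phase 2 study without overall Type I error control. A shift of a fraction of a subject is very unlikely to change a conclusion.

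These points hold the severity at minor. They do not remove the reason to act, because the better method costs almost nothing.

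**Conclusion.** The point holds as a minor improvement. If SF and AP are imputed in separate runs and their residual correlation given own history, treatment and strata is positive, NRI-C understates clinical remission per SF/AP by roughly 1 to 7 points among COVID-imputed subjects. At 10% missing this is about 0.1 to 0.7 points on an arm rate and about 0.3 points or less on the risk difference. The correlation, success rates and missing share behind these sizes are all assumed.

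A reader might infer two stronger things that the documents do not support.

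1. That the SF-AP correlation is lost altogether. It is not: the treatment, strata and own-history terms in 9.2.1 carry part of it (0.15 to 0.245 of a true 0.4 above). Full independence is a limiting case, in which the shortfall reaches about 10 points.
2. That the error shrinks the ABBV-154 minus placebo difference. The shortfall is largest when each component succeeds about half the time and falls on either side, so the difference can move either way.

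For the SF/AP response and enhanced response endpoints the net direction is uncertain, because they combine an either-component rule with a requirement that both be no worse than Baseline.

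**What to change.** State in SAP 9.2.1 that SF and AP are imputed together: one MCMC step and one PROC MI call containing Baseline and all post-baseline values of both variables for the period, with one seed pair. Derive remission, clinical response and enhanced clinical response per SF/AP from the same imputed data sets. Replace the SF and AP rows of the Appendix E table by one row.

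Adding only the other component's past values to two separate runs would not be enough, because the same-visit residuals would still be drawn independently.

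The cost is SAP wording, one merged table row and one merged program step, with a somewhat larger imputation model. It needs no new data and leaves the estimand unchanged. If the sponsor already intends joint imputation, saying so and merging the two rows settles the matter.

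### NRI-C imputes SES-CD as 20 ordinal 0–3 subscores by linear regression and rounding, which misclassifies COVID-19-missing subjects on endoscopic endpoints, though the effect on whole-trial results is small

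*SAP*

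**What the plan says.** - SAP Appendix E (Table I-1) gives the SES-CD entry as "SES-CD (for 20 individual variables", with one PROC MI seed and no MCMC seed.
- SAP 9.2.1 on the method: "PROC MI will be used to generate 30 datasets using the regression method", and "If the binary endpoints are derived from the continuous variables, PROC MI will be applied to the continuous variables".
- SAP 9.2.1 on the predictors: "treatment group, randomization stratification factors for the corresponding period, age, gender, weight, baseline measurement (if applicable) and post-baseline measurements at each visit". It does not say whether the other 19 subscores enter the model for a given subscore.
- SAP 9.2.1 on the draws: "The imputed post-baseline measurements will be rounded to the same precision as the observed data before the determination of responder status". It gives no minimum, maximum, ordinal model or matching step, and does not say what happens to a value that rounds to −1 or 4.
- SAP Appendix C scores four variables in five segments, each from 0 to 3.
- SAP 3.0 defines ulcer-free endoscopy as "SES-CD ulcerated surface subscore of 0 in subjects with SES-CD ulcerated surface subscore" of at least 1 at Baseline. Endoscopic remission requires, among other things, "no subscore > 1 in any individual variable".
- Under SAP 9.2.1, multiple imputation applies only to COVID-19-missing values. Other missing data, and data after confounding medication, become non-response.
- NRI-C is the main analysis for the primary endpoint (9.3.2), the secondary endpoints (9.4.1) and, in Induction and randomized Maintenance, the other binary endpoints (9.5).

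**The concern.** Endoscopic subscores cluster at 0, especially after successful treatment. The regression method adds a normal residual of constant spread to each predicted subscore. Some draws then round to 1 or 2, and others to −1. An endpoint that needs five subscores to be exactly 0, or all 20 to be at most 1, fails if a single draw strays.

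SAP 9.2 says the COVID-19 exception is there to give reliable treatment-effect estimates as if the pandemic had not interfered. If an imputed subject can hardly ever be ulcer-free, the exception does no work for that endpoint. The same imputation also feeds the Week 12 primary endpoint, the Week 40 secondary endpoint, and the response rates used for dose-response modeling (9.6). Because out-of-range handling is not specified, two programmers could follow the SAP and obtain different primary results.

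**Working it through.** **1. The plan's own figures.** The documents give no figure for the imputation. Their power statements fix the response scale (SAP 2.4): 11% against 11 + 26 = 37%, two-sided alpha 0.1. A normal-approximation chi-square calculation gives 94.1% power with 53 per group and 87.1% with 40 per group, consistent with the stated "more than" 90% and 80%.

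**2. A direct check for ulcer-free endoscopy.** Take the most favorable subject, with a predicted ulcerated-surface subscore of exactly 0 in all five segments and independent residuals. The chance that all five draws round to 0 is [P(|Z| < 0.5/SD)]^5. With an assumed residual SD of 0.4, 0.5 or 0.7 this is about 31%, 15% or 4%.

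**3. Simulation of the stated rule.** Twenty subscores of 0–3 were generated, COVID-19-missing scores deleted, and Bayesian linear-regression draws rounded to integers. Assumed, not in the documents: baseline SES-CD averaging about 16, the item distributions, and the missing fraction. The SAP's predictor list allows two readings: each item's own baseline only ("own"), or all items jointly ("all").

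Among imputed subjects (%, or points for the response difference), true → own / all:

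| Setting | Ulcer-free | Remission | Response difference |
|---|---|---|---|
| Week 12, 5% missing | 12.8 → 0.4 / 0.5 | 23.0 → 4.4 / 14.9 | 27.0 → 18.7 / 16.2 |
| Week 12, 10% missing | 13.9 → 0.4 / 0.7 | 24.7 → 4.7 / 15.0 | 28.2 → 18.8 / 12.6 |
| Week 40, 5% missing | 10.1 → 0.3 / 0.5 | 20.3 → 4.6 / 12.2 | 26.3 → 22.2 / 13.3 |
| Week 40, 10% missing | 10.4 → 0.4 / 0.5 | 20.0 → 4.8 / 13.4 | 22.2 → 22.5 / 13.1 |

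The loss of remissions runs from 1 − 13.4/20.0 = 33% to 1 − 4.4/23.0 = 81%. A second simulation with other assumed distributions gave, among imputed ABBV-154 subjects, ulcer-free 1.5% (true 17%) and remission 8–15% (true 23%).

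**4. Whole-trial effect.** Shift ≈ missing fraction × (imputed rate − true rate). For example, Week 40 remission at 10% missing, own-baseline: 0.10 × (4.8 − 20.0) = −1.5 points. Week 12 response difference at 10% missing, all items: 0.10 × (12.6 − 28.2) = −1.6 points. The simulated whole-trial values agree. NRI-NC, which counts COVID-19-missing as failure, is in parentheses:

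| Setting | Ulcer-free | Remission | Response difference |
|---|---|---|---|
| Week 12, 5% | 12.9 → 12.3 / 12.3 (12.2) | 23.8 → 22.8 / 23.3 | 25.6 → 25.1 / 25.0 (24.2) |
| Week 12, 10% | 12.8 → 11.5 / 11.5 (11.4) | 23.6 → 21.7 / 22.7 | 25.6 → 24.7 / 24.1 (22.8) |
| Week 40, 5% | 11.6 → 11.1 / 11.1 (11.1) | 21.7 → 20.9 / 21.3 | 25.9 → 25.7 / 25.2 (24.5) |
| Week 40, 10% | 11.4 → 10.4 / 10.4 (10.3) | 21.3 → 19.8 / 20.6 | 25.5 → 25.6 / 24.6 (23.4) |

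Remission falls by 0.4–1.9 points. The response difference moves by about 0–1 point, reaching 1.5 points at Week 12 with 10% missing and all items in the model. For ulcer-free, NRI-C is within 0.1 point of NRI-NC throughout.

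**5. Candidate repairs, imputed subjects, 5–10% missing.**
- Clipping to 0–3: response difference about 4–10 points against a true 22–28, remission about 2–11%, ulcer-free about 2–5%. At 10% missing the whole-trial response difference falls to 23.2–23.8 (Week 12, true 25.6) or 23.9–24.1 (Week 40, true 25.5).
- Linear regression of total SES-CD: response difference about 15–17 points. In the second simulation, imputed placebo response was 18% against a true 8%.
- Whole-vector predictive mean matching: Week 40 at 10% missing gives ulcer-free 11% (true 10%), remission 21% (true 20%) and response difference 24 (true 22). Week 12 at 10% missing still shows some shrinkage of the difference, 23 against 28, but the whole-trial difference is 25.1 against 25.6.
- Direct binary imputation, second simulation: response 10% and 29% (placebo, ABBV-154) against a true 8% and 28%. A further simulation of logistic imputation gave ABBV-154 remission 22% (true 21%) and ulcer-free 15% (true 13%).

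**The case against.** The strongest reply is that imputation touches only COVID-19-missing values, so the trial's results barely move. That stands. A reader might infer that trial-level remission is halved or that the Week 40 treatment difference is badly distorted. The documents do not support either: SAP 9.2.1 overrides every other kind of missing data with non-response, and the large errors exist only among imputed subjects. At Week 40 the response difference is even nearly right if each item is predicted from its own baseline alone.

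The SAP also does not say the draws are unbounded, nor that all 20 baseline and the other post-baseline items enter each regression. Those are readings of its silence. Bounding would not rescue the method, because the cause is a normal residual on ordinal items that are mostly 0.

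NRI-NC and as-observed analyses are planned for the primary and secondary endpoints (9.3.3, 9.4.2), and in the simulation NRI-NC moves the response difference further than NRI-C does. Remission and ulcer-free endoscopy are other endpoints (3.3), in a Phase 2 study without Type I error control. All of this limits the consequence. But NRI-NC cannot reveal the ulcer-free error, because NRI-C gives almost the same answer for that endpoint.

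One might extend the point to absence of bowel urgency and rectal bleeding, which Appendix E also lists for imputation. SAP 3.0 defines neither endpoint. In a simulation of urgency, counting imputed values of 0 or below as absence removed the error; bleeding was not simulated. Those endpoints need a stated rule, not a new method.

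**Conclusion.** The point holds in limited form. The stated method is wrong for these items: among COVID-19-missing subjects it makes ulcer-free endoscopy almost impossible (0.3–1.5% against a true 10–17%) and loses about a third to four fifths of remissions. It can shrink the imputed response difference at both Week 12 and Week 40, by an amount that depends on a model choice the SAP leaves open. For ulcer-free endoscopy, NRI-C collapses to nearly plain non-responder imputation, contrary to the aim in SAP 9.2.

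At an assumed 5–10% COVID-19 missing, the consequence for reported results is small: about 0–1 point on the response difference (1.5 at worst) and 0.4–1.9 points on remission. The documents give neither the COVID-19-missing fraction nor the item distributions, so all sizes rest on assumption. At 20% missing at Week 40, the response difference would go from 25.2 to 23.1–24.5 and remission from 21.4% to 18.0–19.8%. The correction is worth making because it is cheap and removes an unspecified choice from the primary analysis.

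**What to change.** In SAP 9.2.1 and Table I-1, replace the 20-item linear regression with one of two methods:

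- Impute each binary endoscopic endpoint (response, remission, ulcer endpoints) directly by logistic regression on treatment, stratification factors and baseline SES-CD.
- Use predictive mean matching of the whole 20-item vector, with donors from the same treatment group, so that every imputed set of subscores is one that was actually observed.

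Do not rely on clipping to 0–3 or on linear regression of the total score.

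The cost is SAP wording and code. SES-CD is collected at only one post-baseline visit per period (SAP 9.1), so direct binary imputation loses no longitudinal endoscopic information. Its small downside is that one subject's separately imputed endpoints need not agree with each other; whole-vector matching avoids this.
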